#### Materials and Equipment

The materials being used in training session were posters, dental model, tooth brush, rinsing glass, and water bucket. The examiner collected the data using probe, mouth-mirror, microbrush, disclosing solution, kidney-basin, cotton roll, mask, gloves, rinsing glass, bucket, table, and chairs. The data of the examination and interview was collected using examination forms, questionnaire, and a pen, while the tooth brushing video was recorded using smartphone and the data was written in observational sheet. The materials for reinforcement sessions were dental model, tooth brush, rinsing glass, bucket, and mirror. Additionally, child size tooth brush and tooth paste were given for each participant.

#### Dependent Variables and Data Collection

The dependent variables in this study were Plaque Index (PI) and Gingival Index (GI). The hypotheses of this study were the plaque level and gingivitis level in subjects using the Modified Circular method is different from that in subjects using natural tooth brushing method and the level of plaque after using the Modified Circular method is different from that before using the method.

*Plaque Index Examination.* Participants' plaque level was measured using Turesky Modification of Quigley Hein (83). Data were collected during baseline and follow-up to track the changing of the plaque level before and after intervention. The tools used in this examination were micro-brush, mouth mirror and probe under the natural light. The procedure was painting all of the exposed tooth surfaces with disclosing solution and the participants were asked to rinse one time. Facial and lingual surfaces of the teeth were examined except third molars. A score between 0 and 5 was given based on the criteria. The plaque scores were recorded on the plaque index examination sheet containing the diagram of the teeth with the separated boxes of facial and lingual/palatal areas. The index was determined by calculating the total score divided by the numbers of the surfaces examined.

Table 1 Scoring criteria of Turesky Modification of Quigley-Hein Index (83)

Score	Criteria
0	No plaque.
1	Separate flecks of plaque at the cervical margin of the tooth.
2	A thin continuous band of plaque (up to one mm) at the cervical margin of the tooth.
3	A band of plaque wider than one mm but covering less than one-third of the crown of the tooth.
4	Plaque covering at least one third but less than two thirds of the crown of the tooth.
5	Plaque covering two-thirds or more of the crown of the tooth.

*Gingival Index Examination.* The examination of gingival condition was using the Gingival Index (88). Data were collected during baseline and follow-up to track the changing of the gingival condition before and after intervention. The tools used in this examination were mouth mirror under the natural light. The procedure was examining all of the gingiva on the buccal, lingual/palatal, mesial, and distal areas of the teeth. A score between 0 and 3 was given based on the criteria. The Gingival Index were recorded on the gingival index examination sheet containing the diagram of the teeth with the separated boxes of buccal, lingual/palatal, mesial, and distal areas. The index was determined by calculating the total score divided by the numbers of the areas examined.

Table 2 Scoring criteria of Gingival Index (88)

Score	Criteria
0	Normal gingiva.
1	Mild inflammation - slight change in color, slight edema. No bleeding on probing.
2	Moderate inflammation - redness, edema and glazing. Bleeding on probing.
3	Severe inflammation - marked redness and edema. Ulceration. Tendency to spontaneous bleeding.

*Questionnaire.* Personal information; oral health knowledge, attitudes, practices; and eating habits of the participants were recorded using questionnaire. The questionnaire were questioned by interview. Data were collected during baseline and follow-up to check the changing of tooth brushing practice and eating habit that may influence the plaque and gingival index. The back-translation technique had been used to ensure the quality between the English and Indonesian language versions. The interviewer marked

X on the box of questionnaire choice of answers in accordance with the answers of participants.

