#### Data collection procedure

- 1) The researchers well informed the teachers, parents or guardians, and the children about the purpose of the study, the procedure, and the right to continue or withdrawn without any penalties. The parents or guardians of the children who meet the inclusion criteria were asked by the researcher and teachers the permission to their children to participate in this study. Their consent were shown by signing of the consent form.
- 2) The appointment were made with the teachers to set the time to perform examination and intervention to the children.
- 3) Baseline data collection were done to all of the student participating of the study. The children were interviewed by interviewee using structured-questionnaire inside of the class. The oral examinations were done after completing the interview. The oral examination began with the examination of gingival condition and then continued with plaque level examination. Examination area was set outside of the class to get enough light. The children were examined on a chair in sitting position using natural sun light. The examiner was blind to the allocation of the group, the examiner will not know whether the group examined was intervention group or control group. After the oral examination was done, the video recording was taken to the children to record the way the children brush their teeth. The area recorded was only around their mouth and not showing their face.
- 4) In the other day, children in each group were given 2 hours for tooth brushing training course in small groups containing 4-5 children per group. The instructor motivated the children about how to improve oral hygiene for both groups. The

children were instructed to brush their teeth two times per day in two minutes. The control group were instructed to brush the teeth as how they brushed every day. The intervention group were demonstrated about how to brush the teeth using Modified Circular method. After the training in the class was completed, the activity then continued with practiced brushing together in schoolyard. Intervention group were observed once a week to make sure that they did Modified Circular method well without any repetition or addition of intervention. The researcher provided toothbrush and toothpaste to be used by the children during the one-month intervention period.

- 5) Follow up examination were done one month after the training by collecting the same data as baseline.

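### Was the Gingival Index scored without the probe that its own criteria call for?

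*Combined protocol and SAP*

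**What the plan says.** All references are to the combined protocol and SAP.

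- **Gingival Index tools** (Dependent Variables and Data Collection): "The tools used in this examination were mouth mirror under the natural light".
- **Gingival Index procedure** (same section): "The procedure was examining all of the gingiva on the buccal, lingual/palatal, mesial, and distal areas of the teeth". Scoring is then described as "A score between 0 and 3 was given based on the criteria".
- **Table 2, score 1**: mild inflammation, with "slight change in color, slight edema. No bleeding on probing".
- **Table 2, score 2**: "Moderate inflammation - redness, edema and glazing. Bleeding on probing".
- **Examiner's kit** (Materials and Equipment): "The examiner collected the data using probe, mouth-mirror, microbrush, disclosing solution", followed by further items.
- **Plaque Index tools** (Dependent Variables and Data Collection): "The tools used in this examination were micro-brush, mouth mirror and probe under the natural light".
- **Order of examinations** (Data collection procedure): "The oral examination began with the examination of gingival condition and then continued with plaque level examination".

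No section says in so many words that the gingiva was probed, or that it was not.

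**The concern.** The tool sentence and the scoring table appear to conflict. Two of the four scores depend in part on whether the gum bleeds when probed, yet the only instrument named for this examination is a mirror. The Plaque Index sentence, built the same way, does name a probe, although none of the six scores in Table 1 mentions probing. The contrast could therefore be read as deliberate: probe for plaque, mirror for gingiva. Since the gingiva was examined first, plaque probing is not described as supplying the bleeding sign either.

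If the gingiva was never probed, the line between scores 1 and 2 was drawn by eye. The lower mean index reported for the intervention group in section 8 would then belong to a visual variant of the index and not to the one in Table 2. That would matter, because the Gingival Index carries general objective b and specific objective b.

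**Working it through.** The plan states no figure to reproduce, so the check sets the relevant statements side by side and then asks how far a visual-only score could reach.

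**1. Was a probe at hand?** Yes. Materials and Equipment lists it first among the items the examiner used to collect data. It is not assigned to either index there. Data collection procedure describes the two oral examinations as consecutive, so the instrument was available when the gingiva was scored.

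**2. Was the bleeding sign part of the scoring?** The text says scores 0 to 3 were given according to the criteria. Those criteria include bleeding on probing. Taken at face value, this implies that the sign was assessed.

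**3. Are the tool sentences complete lists?** The Plaque Index sentence can be tested. It names micro-brush, mirror and probe, but not the disclosing solution, which the next sentence has the examiner painting onto the teeth and which Materials and Equipment lists. One may call the solution a material and not a tool. Even so, absence from such a sentence is weak evidence that something was not used. The Gingival Index sentence also uses a plural for a single item and does not say that nothing else was used.

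**4. How much of the index depends on probing?**

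| Score | Visible signs in Table 2 | Probing mentioned |
|---|---|---|
| 0 | normal | no |
| 1 | slight colour change, slight edema | yes (no bleeding) |
| 2 | redness, edema, glazing | yes (bleeding) |
| 3 | marked redness and edema, ulceration | no (spontaneous bleeding) |

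Probing appears in 2 of 4 scores, and those two also differ on visible signs. Without a probe, an examiner would still have a basis for separating 1 from 2, though not the full one.

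**5. What could a visual-only score do to the comparison?** The index is the total score divided by the number of areas examined. Moving one area between scores 1 and 2 changes its score by 2 − 1 = 1. If *f* is the net fraction of a group's areas scored 1 that probing would have made 2 (negative if the net movement is the other way), that group's mean is too low by *f* × 1 = *f*, taking each child to have the same number of areas. The difference, control minus intervention, then shifts by *f*(intervention) − *f*(control), which is zero when the two fractions are equal. The documents give no Gingival Index means or score distributions, so neither fraction can be filled in, and neither the direction nor the size of a shift can be derived.

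**6. Could the omission alone create a group difference?** The description of the examination is common to both schools, and Experimental Design and Data collection procedure both state that the examiner was blind to allocation. On that description, the omission would bear on what the difference measures. It does not by itself explain why there is one.

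**The case for a change.** The best argument for acting is that nothing in the documents closes the question. A probe in the kit shows availability, not use on the gingiva, and the only examination to which a probe is expressly tied is plaque. The Gingival Index kappas under Validity and Reliability, 0.73 between raters and 0.76 within the examiner, do not help, since two readings can agree on a purely visual score and the section does not say how the gingiva was examined at calibration. A reader wishing to repeat the measurement would have to guess, and a clarifying sentence would cost almost nothing.

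All of that stands as a comment on reporting. It does not stand that the described procedure cannot yield the index in Table 2: the description includes scoring by the criteria, and the needed instrument was in the kit. The serious consequence, a Gingival Index result that is not on the stated index, arises only if the probe was not used, and no section says that.

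**Conclusion.** This is most likely a clerical omission from a tool list. The discrepancy is genuine, but the kit list, the statement that scoring followed the criteria, and the incompleteness of the parallel plaque sentence all favour the reading that the probe was simply not named. On that reading one word is missing, and no analysis, estimate or conclusion changes.

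The conclusion rests on two assumptions: that the examiner scored by Table 2 as stated, and that the procedure was the same at both schools and both examinations. The evidence leans towards omission without proving it. If the first assumption were shown to be false, the boundary between scores 1 and 2 would rest on visible signs, and the Gingival Index result in section 8 would need that qualification. The documents contain nothing that asserts this, so no change to the plan follows.

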### Validity and Reliability

*Validity.* Questionnaire had been evaluated for the content, scoring criteria, and language compatibility by three experts from Faculty of Dentistry, Prince of Songkla University using the face validity.

Standardization of oral examination (Plaque Index and Gingival Index) had been evaluated between the examiner and the expert using Cohen's Kappa index. For the Gingival Index, the value of inter-rater calibration was 0.73. The value of intra-rater calibration of Plaque Index was 0.77. All of the values were exceeding 0.7 and categorized as good by Altman (1999).

*Reliability.* The reliability of intra-examiner had been evaluated using Cohen's Kappa Index. The value were 0.76 for the Gingival Index and 0.79 for the Plaque Index. The values were exceeding 0.7 and categorized as good by Altman (1999).

### Experimental Design

The research was using a quasi-experimental study design. Data were gathered from two groups of subjects. This research was a single-blind study which the examiner will be blinded to the allocation of subjects.

This study began with selecting two elementary schools in the same district in Yogyakarta, Indonesia, that have similarity in socio-economic status and the number of the students based on the data and recommendation of Technical Education Service Unit of Yogyakarta. The schools met the criteria that was not under any plans of getting other interventions of dental health program during one month intervention period of this study. All of the fifth graders of the selected schools participated the study. With the coin flipping method, a school was allocated to be intervention group and the other was being the control group. The participants had been informed about the purpose of the study, the procedure, and the right to continue or withdrawn without any penalties. The participants had given consent to follow the study.

The study began with the baseline data collection. Then it continued with the training for the participants about improving the oral hygiene. In this stage, the intervention group was demonstrated and instructed to brush their teeth using Modified Circular method, while the control group was not given any instruction to brush their teeth using a specific tooth brushing method and asked to brush their teeth using the way they brushed every day. The period of intervention was started after training and lasted for one month. In intervention period, intervention group was observed once a week to ensure that they brushed their teeth correctly using Modified Circular method. Finally the evaluation was implemented after 1 month of intervention.

#### Data collection procedure

- 1) The researchers well informed the teachers, parents or guardians, and the children about the purpose of the study, the procedure, and the right to continue or withdrawn without any penalties. The parents or guardians of the children who meet the inclusion criteria were asked by the researcher and teachers the permission to their children to participate in this study. Their consent were shown by signing of the consent form.
- 2) The appointment were made with the teachers to set the time to perform examination and intervention to the children.
- 3) Baseline data collection were done to all of the student participating of the study. The children were interviewed by interviewee using structured-questionnaire inside of the class. The oral examinations were done after completing the interview. The oral examination began with the examination of gingival condition and then continued with plaque level examination. Examination area was set outside of the class to get enough light. The children were examined on a chair in sitting position using natural sun light. The examiner was blind to the allocation of the group, the examiner will not know whether the group examined was intervention group or control group. After the oral examination was done, the video recording was taken to the children to record the way the children brush their teeth. The area recorded was only around their mouth and not showing their face.
- 4) In the other day, children in each group were given 2 hours for tooth brushing training course in small groups containing 4-5 children per group. The instructor motivated the children about how to improve oral hygiene for both groups. The

children were instructed to brush their teeth two times per day in two minutes. The control group were instructed to brush the teeth as how they brushed every day. The intervention group were demonstrated about how to brush the teeth using Modified Circular method. After the training in the class was completed, the activity then continued with practiced brushing together in schoolyard. Intervention group were observed once a week to make sure that they did Modified Circular method well without any repetition or addition of intervention. The researcher provided toothbrush and toothpaste to be used by the children during the one-month intervention period.

- 5) Follow up examination were done one month after the training by collecting the same data as baseline.

## **7. Statistical analysis**

All of the data were analyzed using IBM SPSS Statistics 21. The data gathered from the control and the groups were compared using t-test for the mean and standard deviation. A chi-square statistic were used to investigate whether distributions of categorical variables differ from one another. The significance level used in this study was 0.05 for all of the statistical test.

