#### 4. Conceptual Framework

## 5. Objectives

### General objectives

- a. To compare level of plaque of children aged 10-12 years old that use the Modified Circular method and natural tooth brushing method.
- b. To compare level of gingivitis of children aged 10-12 years old that use the Modified Circular method and natural tooth brushing method.

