## 6. Research Procedures

### Participants and setting

One hundred and twenty four students from two state elementary school in Yogyakarta, Indonesia participated in this study. The age of the participants were between 10 and 12 years old including males and females students. All of the participants were fifth graders from Caturtunggal IV State Elementary School and Babarsari State Elementary School. To be eligible to participate in this study, each participants met the criteria including: students with age 10 to 12 years old and willing as well as permitted by the parents/guardian to join thorough the study. The exclusion criterias were not being discovered from them, that were being diagnosed having developmental disorder, using orthodontic appliances, and using antiseptic mouthwash for daily use.

Caturtunggal IV State Elementary School and Babarsari State Elementary School are the government's schools that are placed in the same cluster in one sub-district. These two schools have the similar characteristics in social-economy, number of students, and

the type of school based on the data and recommendation from Education and Culture Office of Sleman District, Yogyakarta, Indonesia. The examinations were done in the terrace in front of the classes to get the sufficient lighting. The training session was done in the class and the schoolyard. Examination and training each lasted approximately 15 minutes and 60 minutes. The examinations were done two times; before and after training with a distance of one month. While the training session were given one time each group after baseline examination. The reinforcement sessions were given to the intervention group once a week in a month after the training session. The reinforcement sessions lasted approximately 20 minutes for each session.

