## **8. Results**

At the beginning of the study, participants who participated in this study amounted to 62 children for control group and 62 children in experimental group. There was no number of excluded participants. The schools was not under any plans of getting other interventions of dental health program during one month intervention period of this study. After random assignment of the groups, all of the participants received the intervention. Lost to follow-up were found with the number of 2 in control group and 4 in intervention group. The participants did not come in the day of follow-up data collection with the reason of sick and family occasion. Using the intention-to-treat method, the number of data analyzed were following the original number allocated, that were 62 for each group. The missing value in follow-up were replaced using the last value obtained, in this case the baseline value was used.

The age of the participants and the percentage of male and female participants between control and intervention group were not significantly different ( $P < 0.05$ ). The

tooth brushing habit of the participants seen from the frequency and the duration of brushing were not significantly different ( $P < 0.05$ ). Snacking and eating frequency that reflected the eating habit of the participants were also not different ( $P < 0.05$ ).

In this study, all of the participants (100%) in the control group can follow the protocol to brush their teeth using natural method. In intervention group, 79% of the participants followed the protocol to brush their teeth using Modified Brush tooth brushing method systematically.

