### ***Plaque index***

Mean of plaque index for all surfaces in baseline were not different ( $P > 0.05$ ). Analyzed from each surface of each sextant, right and left upper lingual posterior surfaces had statistically different mean plaque index ( $P < 0.05$ ) with the higher number of dental plaque in intervention group. However, the anterior upper labial surface of control group had approximately 0.4 points higher number of plaque index than the control group ( $P < 0.05$ ). In follow up mean of plaque index for all surfaces were significantly different ( $P < 0.05$ ) between groups. All of the mean plaque index in intervention group analyzed from every sextant had lower score than the control group and almost all of them were statistically significant ( $P < 0.05$ ).

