### ***Gingival Index***

In baseline, there was no differences in mean of plaque index between groups ( $P > 0.05$ ). The intervention group had significant lower mean of gingival index than the control group ( $P < 0.05$ ).

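### With one school per arm and a child-level t-test, method and school effects cannot be separated, and the 0.05 level holds only if the between-school ICC is zero.

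*Combined protocol and SAP*

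**What the plan says.** The first general objective is a comparison of brushing methods: "To compare level of plaque of children aged 10-12 years old that use the Modified Circular method and natural tooth brushing method". The second asks the same about gingivitis.

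Under Experimental Design the study is called quasi-experimental and the allocation is described: "With the coin flipping method, a school was allocated to be intervention group and the other was being the control group". Section 8 gives the size of each group: participants "amounted to 62 children for control group and 62 children in experimental group". It also says that all 62 per group were analysed, with baseline values standing in for the six children lost to follow-up.

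Section 7 gives the between-group method in one sentence, "The data gathered from the control and the groups were compared using t-test for the mean and standard deviation", with a significance level of 0.05 for every test. It names no school term, ICC, design effect or baseline adjustment, and no limitation arising from allocation by school.

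The results rest on this test. For plaque: "In follow up mean of plaque index for all surfaces were significantly different". For gingivitis: "The intervention group had significant lower mean of gingival index than the control group". Both are reported only as P < 0.05.

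**The concern.** There are two linked problems.

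**Confounding.** All children taught the Modified Circular method attend one school and all controls attend the other. Anything particular to a school that affects plaque or gingivitis during the month goes entirely into the apparent method effect.

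**Error rate.** The t-test treats the 124 children as independent. Children in one school share influences, and the child-level standard error does not count the variance between schools. The P values are then too small for any between-school ICC above zero.

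Both general objectives depend on this comparison. With only P < 0.05 reported, a reader cannot tell a result that would vanish with a trivial school effect from one that would survive a substantial one. The before-after objectives within the intervention group are a different contrast and are not covered here.

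**Working it through.** **Inputs from the documents**
- Children per school: m = 62 (section 8).
- Schools per arm: 1 (Experimental Design).
- Significance level: 0.05 (section 7). Sidedness is not stated; two-sided is assumed because the hypothesis is non-directional.
- Section 7 does not name the child as the unit. The 62 analysed per group show it, and a school-level t-test would have 2 − 2 = 0 degrees of freedom.

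**Assumed:** the between-school ICC, shown as a range because the documents give none.

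**Reproducing the plan's figure.** With 62 + 62 − 2 = 122 degrees of freedom the critical t is 1.980. At ICC = 0 the type I error is 5.0%, as the plan intends.

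**Effect of a non-zero ICC.** With one school per arm, the true standard error of the difference is the t-test standard error multiplied by

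k = sqrt((1 + 61 × ICC) / (1 − ICC)).

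Example at ICC 0.01: (1 + 0.61)/0.99 = 1.626, so k = 1.275.

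Type I error = 2 × P(T₁₂₂ > 1.980/k). To stay significant, the child-level t must exceed 1.980 × k.

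| ICC | k | Type I error | t needed | Child-level P needed |
|---|---|---|---|---|
| 0 | 1.00 | 5.0% | 1.98 | 0.05 |
| 0.001 | 1.03 | 5.7% | 2.04 | 0.043 |
| 0.005 | 1.15 | 8.6% | 2.27 | 0.025 |
| 0.01 | 1.28 | 12.3% | 2.52 | 0.013 |
| 0.02 | 1.51 | 19.1% | 2.98 | 0.0035 |
| 0.05 | 2.06 | 34.0% | 4.09 | 0.00008 |
| 0.10 | 2.81 | 48.2% | 5.56 | 0.0000002 |

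Simulation with 40,000 runs per value gave unadjusted error rates of 12.1%, 19.3%, 33.9% and 48.6% at ICC 0.01, 0.02, 0.05 and 0.10. Multiplying the standard error by k brought these back to 4.9%, 5.1%, 5.0% and 4.9%.

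**ICC at which significance is lost.** Setting k² = R, where R = (t/1.980)², gives ICC = (R − 1)/(61 + R).
- P = 0.04: t = 2.076, R = 1.100, ICC = 0.100/62.100 = 0.0016.
- P = 0.01: t = 2.617, R = 1.747, ICC = 0.747/62.747 = 0.012.
- P = 0.001: t = 3.372, R = 2.902, ICC = 1.902/63.902 = 0.030.

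**Can the data supply the ICC?** No. There are 0 degrees of freedom between schools within arm. A randomization test on one coin flip has two possible allocations, so its smallest one-sided P is 0.5.

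**How much does the baseline comparison exclude?** With 62 per arm, an observed difference of up to 1.980 × sqrt(2/62) = 0.36 SD is non-significant. A true school shift of 0.3 SD with no method effect would be declared significant about 39% of the time.

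**The case against.** The strongest reply is that the schools were not arbitrary draws. The Participants and setting section says: "These two schools have the similar characteristics in social-economy, number of students", and of the same type. Overall baseline plaque did not differ. Neither school was due another dental programme during the month. Both groups received the same motivation, the same advice on brushing frequency and duration, and a brush and paste. The examiner was blinded. Section 8 describes age, sex, brushing and eating habits as not different, although the P < 0.05 printed beside those statements contradicts the wording. The study also calls itself quasi-experimental, and section 8 reports differences without expressly crediting the method.

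Much of this stands. It makes a large pre-existing difference less likely and favours the low end of the ICC range. It does not break the identity of arm and school, and it does not show that one-month change would have been equal in the two schools. The matching was on socio-economic level, size and school type, not oral health.

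Similarity at baseline is also incomplete: "right and left upper lingual posterior surfaces had statistically different mean plaque index", with more plaque in the intervention school, and a third surface differed by about 0.4 points. On the two lingual surfaces a stable school difference would work against the observed result, so this is evidence of imbalance, not of bias in one direction. The baseline sentence under the Gingival Index heading names plaque. That is probably a slip, but it leaves baseline gingival similarity not clearly stated.

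Two technical points are fair. Baseline adjustment would remove stable school differences, though not school-specific change. And zero school ICC is necessary rather than sufficient, because training in groups of 4-5 children may add clustering of its own. Neither rescues the test as planned.

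**Conclusion.** The concern holds. Method and school are fully aliased, and the between-arm tests of Plaque Index and Gingival Index at follow-up have a 5% error rate only if the between-school ICC is zero. At assumed ICCs of 0.01 to 0.10 the error rate is 12.3% to 48.2%; even 0.001 gives 5.7%.

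These figures assume 62 children per school, a two-sided test, and two schools that behave as independent draws from a population with the stated ICC. Matching makes smaller values more plausible, but nothing in the documents fixes the value.

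This does not show that the reported differences are false; a very small P could survive a plausible ICC. It shows that the stated significance level is unsupported and that attribution to the method alone is not identified. As both general objectives rest on this comparison, it must be corrected.

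**What to change.** **Section 7**
1. Add a statement such as: *Allocation was by school, with one school per arm. The t-test P values do not allow for variation between schools, which cannot be estimated from two schools.*
2. Beside each between-arm Plaque Index and Gingival Index difference at follow-up, give a 95% interval equal to the difference ± 1.98 × t-test SE × k. Use k = 1.28, 1.51, 2.06 and 2.81 for assumed ICCs of 0.01, 0.02, 0.05 and 0.10. Label it a sensitivity analysis that does not remove school confounding.
3. Report the exact t and P for each comparison, with the ICC at which significance is lost: (R − 1)/(61 + R), where R = (t/1.98)².

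A mixed model or GEE should not be offered as the remedy; two schools cannot support either.

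**Section 8**

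Describe the allocation as two schools allocated by coin flip. Present the follow-up results as a difference between two schools that is consistent with a method effect but cannot be attributed to the method alone.

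**Cost**

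Wording changes plus arithmetic on means, SDs and t values already produced; no new data or participants. The price is wider intervals, a less favourable significance statement and a weaker claim for the method.
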